### A. BACKGROUND

**Asthma is a major cause of preventable disease burden (PCORI Methodology Standard RQ-3).** More than 25 million people in the U.S. have asthma, including 8% of adults and 9% of children, with significant racial and income disparities in prevalence. Morbidity from asthma is substantial, causing 10.5 million healthcare visits, 479,000 hospitalizations, and 3,100 deaths in 2009. Low income and racial/ethnic minority patients are more likely to experience adverse outcomes, leading to four times as many hospitalizations and five times as many deaths in blacks than whites, and this gap has been increasing. Guidelines recommend controller medications such as inhaled corticosteroids (ICS), leukotriene antagonists (LTA), or combination ICS and long-acting  $\beta_2$ -agonists (LABA) that are proven to improve asthma control and quality of life, prevent exacerbations, and reduce need for oral corticosteroids, emergency department (ED) visits, hospitalizations, and deaths due to asthma. However, many patients do not use daily controller medications, with 14-20% of individuals not filling prescribed controller medications once. Poor adherence to asthma controller medications increases the risk for adverse clinical outcomes. Increased levels of cost-sharing for asthma medications that lead to reduced adherence have also been associated with adverse downstream outcomes such as increased rates of asthma exacerbations, oral steroid bursts, and asthma-related ED visits and hospitalizations.

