**Patients are increasingly faced with high levels of cost-sharing through high-deductible health plans (HDHPs).**

Compared with traditional plans, HDHPs have lower premiums but subject most services to annual deductibles of at least \$1000. HDHP membership more than quadrupled from 2006 to 2015 and 46% of workers now have HDHPs. HDHPs with associated Health Savings Accounts (HSAs) enable enrollees to use pre-tax dollars to pay for medical care. To qualify to include an HSA, HDHPs must have federally-regulated minimum annual deductibles (individual/family: \$1300/\$2600), and must include all care under the deductible except for select preventive services. As of early 2013, over 15 million people had HSA-HDHPs, with rates of uptake increasing rapidly, especially among large employers. HDHPs are also increasingly prevalent among enrollees in the ACA's health insurance exchanges.

**Patients experience substantial barriers to accessing needed medications for chronic conditions such as asthma due to cost-sharing.** Numerous studies suggest that high cost-sharing is associated with lower use of both non-essential and essential health care, including medications for chronic diseases. Among adults reporting difficulty paying medical bills, more than half said they had difficulty paying for prescription drugs. Studies in adults have shown that increased cost-sharing is associated with decreased use of important asthma medications. The few studies in pediatric populations have also shown reduction in use of asthma medications with increased cost-sharing. Evidence is limited on the impact of cost-sharing on rescue medications for asthma. Two studies have found that higher out-of-pocket (OOP) costs for bronchodilators were associated with decreased use for adults and children; our recent work found that higher copayments did not lead to decreased albuterol use for children relative to those without a copayment change, but did result in higher OOP costs (Figure 1).

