**Families are increasingly concerned about OOP costs that can strain family budgets and lead to intra-familial trade-offs.** OOP costs from one family member can lead to delayed/forgone care for other family members, and high family OOP expenditures have been associated with lower rates of initiation of expensive medications. Some data suggest that parents prioritize their children's health care over their own when faced with financial pressures. Our research found that both adults and children are at increased risk for delayed/forgone care due to cost when faced with high deductibles, and that the risk is greater for healthy adults in families with chronically ill children, and for healthy children in families with chronically ill adults. In another study, we found that having a greater number of children in the family increased risk of financial burden among health insurance exchange plan enrollees, the majority of whom had HDHPs.

[figure not shown]
**HDHP enrollees are at risk for cost-related underuse of medications, especially in HSA-HDHPs.** Our research team was among the first to conduct studies of modern HDHPs, including more recent studies using the large, national dataset that we propose to use for the current project. We found that a switch to a HDHP was associated with fewer ED visits and hospitalizations, especially for low socioeconomic status (SES) enrollees; no change in rates of well-child visits and screenings for breast, cervical, and colorectal cancer, all of which were exempt from the deductible; and pronounced reductions in colonoscopy among low SES members. Other early studies of HDHPs without HSAs

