In this project, we intend to evaluate the impact of two important developments in the health insurance landscape, HSA-HDHPs and PDLs, on medication use, clinical outcomes, and patient experiences for adults and children with asthma. We will take advantage of a rolling cohort of over 621,000 adults and 310,000 children with asthma who receive employer-sponsored coverage from a large national insurer between 2004 and 2017. We will employ a rigorous quasi-experimental interrupted time-series (ITS) and difference-in-differences (DiD) designs to examine the effect of being switched by an employer from HSA-HDHPs without PDLs to HSA-HDHPs with PDLs compared to controls who remain in HDHPs without PDLs. We will compare changes in medication use and patient-centered clinical outcomes (asthma-related ED visits and hospitalizations) for adults and children and within families. Qualitative interviews with patients with asthma in HDHPs will provide more in-depth patient-reported data on health care decision making and experiences in these plans, which will inform quantitative analyses. The overarching goal of this research is to provide needed evidence – including data gathered directly from patients – on whether pairing PDLs with HSA-HDHPs can mitigate cost barriers and improve patient-centered outcomes for adults and children with asthma. Our Specific Aims are:

1. To understand health care decision making and experiences of families with asthma under HSA-HDHPs and PDLs
2. To examine the impact of HSA-HDHPs with and without PDLs on use of asthma controller and rescue medications, and on adverse clinical outcomes (asthma-related ED visits and hospitalizations), overall and for vulnerable subgroups (low-income and racial/ethnic minority patients)
3. To examine the extent to which the response to HSA-HDHPs and PDLs is affected by the presence of other family members with asthma or other chronic conditions
4. To examine the impact of HSA-HDHPs with and without PDLs on out-of-pocket (OOP) costs for patients and families with asthma

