### **Conceptual Model Underlying Study Hypotheses**

The theoretical underpinnings of our study derive from Levy and Meltzer's conceptual model of the effect of health insurance on health outcomes, and known causal pathways linking asthma controller medication adherence to short-term complications. In our model (Figure 2), level of medication cost-sharing for patients with asthma is determined by plan type, as follows: 1) HSA-HDHPs without PDLs - full cost-sharing for controller and rescue medications; 2) HSA-HDHPs with PDLs - no cost-sharing for controller and rescue medications; and 3) traditional plans - three-tiered copayments for controller and rescue medications.

We hypothesize that higher cost-sharing in HSA-HDHPs without PDLs leads to decreased adherence to controller medications and decreased rescue medication use (offset by increased need for rescue medications due to suboptimal controller adherence). Reductions in controller medication use can increase asthma exacerbations and short-term complications such as ED visits and hospitalizations. Because a patient's OOP costs contribute to total family OOP cost burden, which can strain family budgets and lead patients to avoid or defer care and further decrease medication use, OOP costs are an additional outcome of interest. We hypothesize that lower cost-sharing due to PDLs, on the other hand, should lead to increased controller medication adherence, less need for rescue medications, fewer asthma complications, and lower OOP costs and family cost burden.

**Figure 2. Conceptual model** illustrating the impact of HSA-HDHPs with and without PDLs relative to traditional plans. Green arrows represent patterns of medication use, with wider arrows representing greater use.

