For **Aims 2-4**, the study population will be drawn from 14 years of data from a large U.S. commercial health plan with membership in all 50 states and annual enrollment of ~30 million members. The eligible population will consist of adults aged 18-64 years and children aged 4-17 years with asthma in a baseline year while insured in a traditional plan; all subjects must have continuous insurance coverage with pharmacy benefits for at least 24 consecutive months. Study subjects must have spent a year in a traditional health plan with no or low deductibles prior to the switch to an HSA-HDHP without a PDL, or have spent a year in an HSA-HDHP without a PDL before switching to an HSA-HDHP with PDL, and then remain enrolled for at least one-year post-switch. Control group members spend a year in a traditional plan or a HSA-HDHP without PDL then remain that plan for at least another 12 months. As study groups for secondary analyses, we will also identify enrollees switching from traditional plans to HSA-HDHPs with PDLs for comparison with those remaining in traditional plans. We will also identify enrollees with other plan types, not just HSA-HDHPs, which appear to have PDLs in that they have lower cost-sharing for asthma medications compared to other non-preventive medications. Based on preliminary findings from qualitative interviews as part of Aim 1 of the project, we have learned the cost of asthma medications is a problem not only for enrollees in HSA-HDHPs but in other types of HDHPs and in traditional plans with low deductibles as well, so we will also identify enrollees who are switched from having no PDL to having a PDL. Each of these groups will be matched with controls who start in the same type of plan and remain in that type of plan without gaining a PDL.

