2. **Use of asthma rescue medications (Aims 2-3):** We will assess use of albuterol and levalbuterol inhalers, the primary asthma rescue medications prescribed to patients, which are subject to the deductible in HSA-HDHPs without PDLs, free in HDHPs with PDLs, and subject to copayments in traditional plans. All albuterol and levalbuterol inhalers are brand-name drugs containing 200 puffs each. We will exclude nebulized versions as these are predominantly used by younger children and do not come in standardized doses. As in our prior study, we will measure the standardized number of inhalers dispensed per month based on National Drug Code (NDC) in pharmacy claims. Given the inter-relationship between rescue and controller medication use, we will also measure the ratio of controller medications to total asthma medications, a metric for which higher values are associated with better asthma control and lower rates of asthma-related ED visits.
3. **Use of spacers and nebulizer machines (Aims 2-4):** Based on input from patients and stakeholders, and with additional input from questions from added questions in the qualitative interview guide in response, we will assess changes in the number of spacers and nebulizer machines received by study patients, based on claims data. We will measure changes in receipt of spacers and nebulizer machines after a switch to an HSA-HDHP vs. remaining in a traditional plan to see if changes in the cost-sharing for these devices leads to a decrease in receipt and an increase in OOP costs to families.
4. **Asthma-related ED visits and hospitalizations (Aims 2-3):** As a measure of potentially avoidable short-term complications, we will measure asthma-related ED visits and hospitalizations that have a primary ICD-10 diagnosis code for asthma.
5. **OOP health care costs (Aim 4):** We will calculate consumer price index (CPI)-adjusted OOP costs for asthma medications and other health services, summing deductible, co-pay, and coinsurance amounts, aggregated into annual measures. Financial burden due to OOP costs will be defined as annual family OOP costs as a percent of family income, with cutpoints of >5% and >10% to indicate financially burdensome OOP costs.

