*Hypothesis (see Figure 2): Enrollees with asthma in HSA-HDHPs without PDLs will have worse adherence to controller medications, greater need for rescue medications, and higher rates of asthma-related ED visits and hospitalizations, with widening of income and racial/ethnic disparities; the addition of a PDL will improve use of controllers and rescue medications, reduce ED and hospitalization rates, and lessen disparities.*

Analyses will compare changes in outcomes from baseline to up to three years of follow-up among 1) asthma patients switched to HSA-HDHPs without PDLs from traditional plans vs. matched patients whose employers remain in traditional plans; and 2) patients switched to HSA-HDHPs with PDLs from traditional plans vs. matched controls remaining in HSA-HDHPs without PDLs. Sensitivity analyses will compare patients switched to HSA-HDHPs with PDLs from traditional plans vs. those who remain in traditional plans to examine the combined impact of both increasing the deductible and gaining a PDL. We will use separate regression models to compare year-to-year changes for each intervention group relative to its matched control group, rather than including all patients in a single model with multiple interaction terms. For secondary analyses of enrollees in the larger set of plan types that include PDLs, we will compare enrollees who are switched from plans with no PDL to plans with a PDL vs. those who remain in plans without a PDL. These analyses will match and adjust for different baseline plan types and deductible levels.

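### When patients leave a traditional plan, asthma ED visits and hospitalizations measure net utilization, so a null or a fall cannot by itself show that asthma did not worsen

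*Combined protocol and SAP*

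**What the plan says.** Specific Aim 2 names its clinical endpoint in a parenthesis: "adverse clinical outcomes (asthma-related ED visits and hospitalizations". Outcomes, item 4 gives the reading: "As a measure of potentially avoidable short-term complications, we will measure asthma-related ED visits and hospitalizations". The other listed outcomes for Aims 2-4 are medication use, devices and out-of-pocket costs.

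The Conceptual Model gives one pathway to these events: "Reductions in controller medication use can increase asthma exacerbations and short-term complications such as ED visits and hospitalizations". The Aim 2 hypothesis in the Analysis plan accordingly predicts, for HSA-HDHPs without a PDL, "higher rates of asthma-related ED visits and hospitalizations, with widening of income and racial/ethnic disparities".

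Three other statements bear on this:

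- A. Background says an HSA-qualified plan "must include all care under the deductible except for select preventive services".
- Study Population requires "a year in a traditional health plan with no or low deductibles prior to the switch to an HSA-HDHP without a PDL".
- A. Background, in the paragraph on cost-related underuse, reports the team's earlier result: "We found that a switch to a HDHP was associated with fewer ED visits". The sentence goes on to hospitalizations and singles out enrollees of low socioeconomic status.

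**The concern.** The exposure changes the price of the outcome. Dearer controllers may worsen asthma and push ED visits and admissions up. The same switch makes an ED visit or admission dearer and may push them down. The plan models only the first route, although its own background reports the second.

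At stake is the clinical conclusion for the switch from a traditional plan to an HSA-HDHP without a PDL. A null could mean stable asthma, or worse asthma offset by avoided visits. The disparity hypothesis is especially exposed: if low-SES enrollees avoid care more, a true widening of clinical harm could appear as no difference or even a narrowing.

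**Working it through.** **1. Is the outcome repriced?** Before the switch, the deductible is absent or low: Description of Comparators says under $500, and the employer criteria in Study Population say under $1000. After it, the federal minimum for an individual is $1300 (A. Background), and ED and hospital care falls under it. On either definition of a traditional plan, the price rises.

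**2. Does the design remove this?** Matching, difference-in-differences and full-replacement employers address selection and shared time trends. The price change is part of the exposure, so it stays in the estimate. The Conceptual Model sets out both a price effect and an offsetting need effect for rescue medication, but not for ED or hospital use. Generalizability and Limitations does not mention it.

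**3. The plan's own figure.** Inputs from Table 3 and Sample Size and Power: baseline 8.4 per 100; 18,000 switched against 72,000 controls; alpha 0.05; 80% power; sidedness not stated. Treating the rate as a proportion:

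SE ≈ √[0.084 × 0.916 × (1/18,000 + 1/72,000)] = 0.00231

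Two-sided detectable difference ≈ (1.960 + 0.842) × 0.00231 = 0.0065. Solved exactly, it is 0.64 points for a fall and 0.66 for a rise. One-sided, it is 0.57 and 0.58. The stated 0.6 is reproduced to rounding.

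**4. Size of the masking (illustration).** Let M be the true relative rise in events from worse asthma and A the share of events not presented because of price. Both are assumptions.

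Observed rate = 8.4 × (1 + M) × (1 − A)

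A true rise of 0.6 points means M = 0.6/8.4 = 7.1%. It is cancelled when A = 1 − 8.4/9.0 = 6.7%.

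Chances of a significant result, two-sided 0.05, 18,000 against 72,000, no allowance for clustering:

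| M | A | Observed per 100 | Difference | Significant rise | Significant fall |
|---|---|---|---|---|---|
| 7.1% | 0 | 9.00 | +0.60 | 73% | <0.1% |
| 7.1% | 5% | 8.55 | +0.15 | 10% | 0.5% |
| 7.1% | 6.7% | 8.40 | 0.00 | 2.5% | 2.5% |
| 7.1% | 10% | 8.10 | −0.30 | <0.1% | 25% |
| 7.1% | 15% | 7.65 | −0.75 | <0.1% | 91% |
| 15% | 0 | 9.66 | +1.26 | >99% | <0.1% |
| 15% | 10% | 8.69 | +0.29 | 25% | 0.1% |
| 0 | 5% | 7.98 | −0.42 | <0.1% | 45% |
| 0 | 10% | 7.56 | −0.84 | <0.1% | 96% |

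**5. The contrast from HSA-HDHP without PDL to HSA-HDHP with PDL.** Here ED and hospital care is under a deductible before and after the switch, so it is not directly repriced. But controller spending counts toward the deductible only without a PDL. At the quoted $140-$307 a month for some inhaled steroids, a regular user would reach $1300 in 1300/307 = 4.2 to 1300/140 = 9.3 months. The price of an ED visit later in the year may therefore still differ between arms.

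**The case against.** The best defence is that Aim 2 asks about the impact on ED visits and hospitalizations, and the analysis estimates exactly that. This stands: the estimate is valid as a net effect, and no passage commits the team to reading a null as no harm. What remains is that item 4 and the hypothesis label the events as complications, with no caveat on price.

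The plan also has partial safeguards. The Aim 2 analysis gives separate example models for any asthma hospitalization and for ED visit counts. The interviews ask about forgone care, and outcomes they suggest may be added where claims allow. The controller-to-total ratio is linked to asthma control. These help, but the ratio's components are repriced by the same switch and the interviews are qualitative.

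The size is assumed: the background result carries no effect size and is not described as asthma-specific. That is correct, and it is why the table is only an illustration.

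Four stronger readings are tempting, and the documents do not support them:

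- *A fall from a traditional plan to an HSA-HDHP with PDL would pass as a PDL benefit.* Against controls remaining in traditional plans, the Analysis plan calls this a sensitivity comparison of the combined effect of a higher deductible and a PDL.
- *The PDL-only contrast is wholly unaffected.* Step 5 shows an indirect route.
- *Hospitalizations are a price-free anchor.* They are under the deductible too, and the earlier work reports that they also fell.
- *Non-asthma ED visits are a clean negative control.* The switch also puts most other medicines under the deductible, so non-asthma morbidity may change as well.

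**Conclusion.** The concern holds for contrasts that start from a traditional plan. There, asthma ED visits and hospitalizations estimate net utilization, and a null or a fall in them cannot by itself be read as no worsening of asthma or no widening of disparities. The reasoning rests on the plan's own account of HSA-HDHP benefits and on the team's own research on HDHP switches, as reported in A. Background. If price only deters use, a rise would remain informative and would, if anything, understate the harm.

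The size is unknown. Under the simple model above, avoidance of about 7% cancels the 0.6-point rise that Table 3 gives as detectable, and larger avoidance reverses the sign.

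On scope, the Analysis plan words comparison 2 as a switch from traditional plans, whereas the Overview, Description of Comparators and Study Population describe a start in an HSA-HDHP without PDL. Taken literally, the Analysis plan wording would bring comparison 2 under this concern too; the passages need reconciling.

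**What to change.** 1. Add oral corticosteroid bursts from pharmacy claims as an exacerbation outcome in Aims 2-3, excluding the chronic users (180 or more days) already defined under Predictors and Covariates. Fix the claims definition in advance. A. Background already lists bursts among the consequences of cost-sharing: "increased rates of asthma exacerbations, oral steroid bursts, and asthma-related ED visits and hospitalizations". State that bursts are less exposed to the ED and hospital price change but not free of it, since they need a prescriber contact and also fall under the deductible.
2. In every contrast starting from a traditional plan, describe ED visits and hospitalizations as net utilization and report them separately. State that absence of clinical harm will not be inferred from a null or a fall in either one alone, and that hospitalizations are also price-affected. Apply the same rule to the income and race/ethnicity analyses.
3. Optionally, run the same difference-in-differences on non-asthma ED visits as a descriptive gauge of general ED avoidance, not as a negative control.
4. Add the price effect to Generalizability and Limitations. Include a note that in the PDL-only contrast the within-year ED price may differ between arms.

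The cost is one more outcome from claims already held, one optional descriptive analysis and some wording. No new data are needed. Bursts reduce the ambiguity but do not remove it.
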